- 9.3.6 Estimates of the response rate based on CR rate, overall response rate (CR and PR) and the tumor control rate (CR, PR, and stable disease (SD)) will be provided together with the exact two-sided 95% confidence intervals. FDG-PET scanning will be incorporated as a component to assess response rate according to current/updated lymphoma restaging guidelines. The probability of a response in each category will be estimated using the proportion of subjects falling into the response category, that is, (number of subjects with response in that category)/(number of subjects evaluated). For progression-free survival and duration of response the Kaplan-Meier procedure will be used to characterize the survivorship function. Median time-to-events and the corresponding two-sided 95% confidence intervals will be provided for each of these variables. In all estimation we will consider using estimators and confidence intervals appropriate for sequential trials along the lines outlined in Cheng and Shen (Biometrics 60, 910-918) and G Yin and Y Shen (Biometrics 61, 2005).

9.4 Safety Analysis.

- 9.4.1 All patients who receive SGN-35 treatment will be included in the safety summaries and analyses. The safety and tolerability of therapy will be examined by: Extent of exposure to SGN-35 (dose, duration, and number of patients), Detailed summary of deaths by time to death (using Kaplan-Meier methods) and by cause of death, Detailed examination of AEs, Laboratory test results, Vital signs or other physical findings.

9.5 Adverse Events.

- 9.5.1 Adverse events will be classified by body system and preferred term using NCI CTCAE v4. Frequency tables at the patient level will summarize events. Frequency tables by category of event (serious, related), and by NCI CTCAE grade will be presented by dose regimen.

9.6 Laboratory Parameters.

- 9.6.1 Descriptive statistics (mean, standard deviation, mean change from baseline) of laboratory values will be presented. Individual patient graphs

will be displayed and reviewed for clinically relevant changes. Laboratory values of WBC, hemoglobin, absolute neutrophils, platelets, ALT, AST, bilirubin, and creatinine will also be summarized by NCI CTCAE grade.

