Table 4; footnote 10	The first 22 patients entered on the study will have a repeat FDG-PET	Adds the word “evaluable” that was previously omitted.	Administrative

Amendment 4 – April 16, 2013 Scientific Review Committee Approval – April 18, 2013			
Section(s) Affected	Prior Version	Amendment 4 Changes	Rationale
Table of Contents, Protocol Summary, Throughout		Formatting was changed throughout. An updated and linked Table of Contents was added. The Protocol Summary was put into a table format.	Formatting and spacing was adjusted throughout to match the new Northwestern University template.
Protocol Summary; Treatment Plan (Sections 5.1, Figure 2; 5.2.8.2 [new section added]; 5.3.2; 5.3.3.8 [new section added]); Section 7.0, Table 4 footnote 15; Section 9.3.2 Statistical Considerations, Phase II Efficacy Analysis	All 6 cycles of AVD treatment needed to be completed in order for patients to continue on the SGN-35 maintenance.	Patients who are determined to be chemotherapy intolerant may be discontinued from AVD, but may still move on the SGN-35 maintenance. Chemotherapy intolerance is now defined in section 5.3.3.8.	It has been appreciated with the initial several patients treated that there is extreme heterogeneity in this patient population including “very elderly” patients who cannot tolerate 6 cycles of chemotherapy.
Treatment Schema (section 5.1)	Indicated PET/CT was due after cycle 6 and again after consolidation.	Clarifies PET/CT is done every 3 cycles. Also clarifies PET/CT is only required for those in PR/SD. CT only is required for this in CR.	Administrative, to match the protocol parameters (Section 7.0).
Section 5.3.3 AVD chemotherapy	This section did not include dose modifications related to changes in creatinine clearance.	Section 5.3.3.6 was added, providing dose adjustments for decreasing creatinine clearance.	This was updated for safety.
Section 7.2 Pre-cycle testing.	Required all pre-study tests to be done within 4 weeks on beginning	Clarifies that the staging bone	These are not critical factors

	study treatment.	marrow and cardiac testing may be done within 3 months prior to starting treatment.	that are not likely to change within 3-4 months of study entry.

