Section 7.7 Ct scan and PET scan; Table 4	Required scans to be done within 4 weeks of starting treatment. CT of the neck was required.	Allows scans to be done within 6 weeks of starting treatment. The CT of the neck is no longer a requirement.	This is a more clinically realistic time parameter and the neck may be assessed clinically.
Section 8.1.6 (SGN-35 Preparation)	Requires drug to be diluted into at 150ml infusion bag.	Removes requirements for 150ml bag.	NMH Pharmacy does not carry 150ml infusion bags, and the size of the infusion bag does not impact the drug.
Section 8.1.7 (Required Premedication and Postmedication)	It was advised that anti-emetics are not to be given prior to the 1 st cycle.	Allows anti-nausea medications as needed.	This was done for standard clinical practice.
Amendment 5 – May 31, 2013			
Scientific Review Committee Approval – June 5, 2013			
Section(s) Affected	Prior Version	Amendment 5 Changes	Rationale
Cover Page		Adds Tufts University as a site.	An additional site is being added to aid in enrollment to the trial.
Section 1.0 (Introduction and Study Rationale)	Section 1.6.5 was not included.	Adds background on the incidence of pancreatitis seen with SGN-35. Also adds a description of the ongoing other trial of SGN-35 for elderly patients.	Additional background and safety information is now available and has been added.
Section 3.3.2	Excluded patients with a history of	Excludes patients	This protocol

(Selection of Patients)	another primary cancer that has not been in remission for at least 3 years, with exceptions indicated.	with no currently active other malignancy other than melanoma. “Currently active” is clearly defined.	includes older patients who often have a prior cancer history. This revision is for clarity.
Section 3.0 (Selection of Patients)	Section 3.3.8 did not exist.	Excludes patients with a history of pancreatitis.	This is being done for patient safety, after a severe, unexpected case of pancreatitis was seen on the study.
Section 3.2 (Exclusion Criteria)	Excludes patients with “any active systemic viral, bacterial, or fungal infection requiring IV treatment with antimicrobial therapy within 1 week prior to first dose.”	Clarifies that this must be infection requiring “ IV treatment.”	Clarification

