Section 5.2.5 (Dose Modifications), including Table 3	Did not include dose modifications specifically related to pancreatic toxicity.	Add dose modifications specifically related to pancreatic toxicity (SGN-35 is to be held until the toxicity resolves).	This is being done for patient safety, after a severe, unexpected case of pancreatitis was seen on the study.
Section 7.0 (Study Parameters)	Did not require amylase or lipase testing.	Amylase and lipase testing was added.	This is being done for safety, due to the pancreatitis case seen on the study. These labs will be used for monitoring for toxicity.
Section 7.0 (Study Parameters); Section 12.0 (Pathology Requirements)	Safety PK specimens were not collected.	Safety PK sample collection has been added.	This is being added as a safety measure in the event a study participants

			experiences an adverse drug reaction.
Section 7.0 (Study Parameters) & Table 4 (Schedule of Activities)	
 1. No windows given for scheduled tests, assessments, and procedures. 2. Table listed tests as being completed “every cycle.” 	
 1. Allows a window of +/- 2 days for all scheduled tests, assessments, and procedures. Allows a window of +/- 7 days between cycles. 2. Changed to “X” with footnotes clarifying “Day 1 (+/- 2 days) of each cycle.” 	
 1. Added to avoid protocol deviations for slight changes in scheduling due to weekends, holidays, etc. 2. Clarity
Section 11.0 (Records To Be Kept)	Required treatment eCRFs, including the summary, to be completed at the end of therapy.	Summary eCRFs are no longer required. Treatment data must now be submitted each cycle.	DMC requires more frequent review of data for compliance and safety. In addition, the new eCRFs negate the needs for a treatment summary sheet, as all data is collected on treatment forms.
Amendment 6 – July 30, 2013 Scientific Review Committee Approval – August 7, 2013			
Section(s) Affected	Prior Version	Amendment 6 Changes	Rationale
1.6.5 (Pancreatitis and SGN-35)	Information regarding SGN-35 and pancreatitis based on data available as of May 9, 2013.	Updates data based on more recent internal review of	Updated for safety reasons per memo from

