		data by Seattle Genetics (as of June 30, 2013) and indicates the intention to update the Investigator's Brochure in the upcoming version, as acute pancreatitis is now considered. an important potential risk associated with SGN-35 dosing.	Seattle Genetics.
Section 5.2.5.1 (Dose modifications regarding pancreatitis)	Instructions referenced drawing lipase depending on results of amylase.	Revises dose modifications to require action based on elevation of either lipase or amylase.	Updated for clarity.
Table 4 (Schedule of Activities)	Only amylase listed on the table for pancreatic monitoring.	Adds lipase.	Lipase was left off by mistake in the last version.
Section 10.5 (Termination of Treatment and/or Study Participation)	Language unclear about follow-up for survival endpoints.	Clarifies that patients who terminated study treatment may be followed for survival endpoints, unless they also withdrawn consent from the study as a whole.	Clarity.

Amendment 7 – November 18, 2014 Scientific Review Committee Approval – November 19, 2014
			
Section(s) Affected	Prior Version	Amendment 7 Changes	Rationale
Cover page		Contact information for sub-investigator [name] updated	Administrative
Cover page		Sub-investigators [name],	Administrative

		MD and [name] deleted	
3.1.6	Patients must have bi-dimensional measurable disease documented within 30 days prior to registration and documented in tumor assessment form. Non-measurable disease must have been assessed within 60 days prior to registration.	Revised to 60 days prior to starting treatment, and removed documentation on the tumor assessment form. Non-measurable disease must have been assessed within 60 days prior to starting treatment.	
3.1.7	Patients must have a bone marrow biopsy (bilateral preferred, unilateral acceptable) within 60 days prior to registration.	Revised to 90 days prior to starting treatment.	
3.1.8	Patients must have a MUGA or echocardiogram within 60 days prior to registration...	Revised to 90 days prior to starting treatment	
3.3.2	No “currently active” other (second) malignancy	Quotation marks removed	Administrative
3.3.5	Patients with HBsAG positive HBV infection	Revised to known HBsAG positive HBV infection	Clarification
4.0	Registration procedures	Patient registration information revised to include most current registration procedures	Administrative

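### Amylase and lipase tests were first required at Amendment 5, but the adverse-event tables cover all SGN-35-treated patients, so any patient without a post-dose value biases the elevation rate downward

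*Combined protocol and SAP*

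**What the plan says.** **Safety population and tables.** Section 9.4.1: "All patients who receive SGN-35 treatment will be included in the safety summaries and analyses". Section 9.5.1: "Frequency tables at the patient level will summarize events", by category and by CTCAE grade. Section 10.2.1 includes abnormal laboratory findings among adverse events. Neither 9.4.1 nor 9.5.1 has a rule for tests that were not done in everyone.

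**Laboratory summary.** Section 9.6.1 plans means, standard deviations, changes from baseline and individual graphs. It adds a by-grade summary for eight named parameters; amylase and lipase are not among them.

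**When testing began (Appendix VII).**
- Amendment 4 (April 2013) shows that treatment was under way: "It has been appreciated with the initial several patients treated that there is extreme heterogeneity in this patient population".
- "Amendment 5 – May 31, 2013" states that the prior version "Did not require amylase or lipase testing", and then "Amylase and lipase testing was added". It also brought in exclusion 3.3.8 (prior pancreatitis) and pancreatic dose-modification rules, "after a severe, unexpected case of pancreatitis was seen on the study".
- Amendment 6 (July 2013) put lipase into Table 4: "Lipase was left off by mistake in the last version".
- Amendment 7 (November 2014) changed the timing footnote from optional to mandatory wording.

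**Current schedule.** Table 4 marks amylase and lipase pre-study, in lead-in and in consolidation, but not during AVD or post-therapy follow-up. Footnote 17 ties the draws to the 72 hours before an SGN-35 dose.

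**The concern.** An asymptomatic enzyme rise can be recorded only in a patient whose blood was tested after a dose. If the table divides by all treated patients, each unmeasured patient is counted as free of the event, and the rate can only move down.

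Safety of the sequence is secondary objective 2.2(b). Section 1.6.5 reports that the manufacturer regards acute pancreatitis as a potential risk of the drug, and a case on this trial led to the new testing. Yet these two enzymes are missing from the by-grade laboratory table, and the one table they can enter has no denominator that reflects who was tested.

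The exclusion of patients with prior pancreatitis is a separate matter. It changes the case mix after Amendment 5, which is a reason to describe the two periods separately, but it is not dilution by unmeasured patients.

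**Working it through.** The plan states no enzyme-elevation rate, so there is no figure to reproduce. The amendment history is used only to date the changes, not as a contradiction of the current text.

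**Step 1: who may lack a post-dose value.**

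| Period | Requirement |
|---|---|
| Before Amendment 5 (31 May 2013) | Neither enzyme required |
| Amendment 5 to Amendment 6 (30 July 2013) | Both said to be added; Table 4 lists amylase only |
| Amendment 6 to Amendment 7 (18 Nov 2014) | Both in Table 4; timing wording optional |
| From Amendment 7 | Both in Table 4; timing wording mandatory |

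The current schedule also leaves a gap. The first draw precedes dose 1, so a patient who stops after one dose may have no scheduled post-dose value and yet is in the safety population.

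**Step 2: could earlier patients be tested later?** Some could. On the planned schedule the first consolidation dose falls 6 weeks (lead-in) + 22 weeks (first to last AVD dose: 5 × 4 + 2) + 2 weeks (Section 5.4.2.1) = 30 weeks after the first lead-in dose. Patients who started within roughly 30 weeks before Amendment 5 could therefore have a draw before consolidation. Two limits apply:
- Consolidation is not given without CR or PR (5.1), after progression before AVD (5.2.8.1), or with neurotoxicity that does not recover in time (5.4.2.4).
- A first value at consolidation misses the lead-in, whereas Section 1.6.5 says that most pancreatitis cases were reported in the first or second dosing cycle.

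**Step 3: size of the bias.** Let N = 48 (planned enrolment, 9.3.1) and k = treated patients with no post-dose value. If risk is equal in measured and unmeasured patients, tabulated rate = true rate × (N − k)/N.

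The documents do not give k or the true rate; both are assumed here. The value 22 is all of stage 1, taken as an illustrative upper value.

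| k | (48 − k)/48 | True 10% appears as | Factor if half of these k are tested later |
|---|---|---|---|
| 0 | 1.00 | 10.0% | 1.00 |
| 5 | 0.90 | 9.0% | 0.95 |
| 10 | 0.79 | 7.9% | 0.90 |
| 15 | 0.69 | 6.9% | 0.84 |
| 22 | 0.54 | 5.4% | 0.77 |

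The direction is downward for every k above zero.

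**Step 4: what a before/after display can show.** At the clinical-programme incidence of 0.27% in Section 1.6.5, the expected number of acute pancreatitis cases is 48 × 0.0027 = 0.13. One or two cases split at an amendment that was itself prompted by a case cannot separate the effect of the exclusion or the monitoring from chance.

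**The case against.** The strongest reply is that the harmed table is not in the plan by name. Section 9.6.1 does not grade amylase or lipase, and its means and changes use available values, so an untested patient cannot enter them as normal. Section 9.4.1 says who is included, not what the denominator is for each test. This is right as far as it goes. But Section 10.2.1 makes an abnormal laboratory finding an adverse event, so elevations reach the patient-level tables of 9.5.1, where all treated patients is the only population defined. The absence from 9.6.1 is a gap in itself.

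Three stronger readings are tempting and not supported:
- *That early patients were never tested.* A test that was not required may still have been done, and some patients could be tested at consolidation. The number unmeasured could be zero.
- *That the plan yields an upper confidence limit that is too low.* Sections 9.4 to 9.6 plan no confidence interval for any adverse-event or laboratory rate.
- *That comparing periods would show whether the exclusion or monitoring changed the risk.* Step 4 shows that it cannot.

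Two further points stand. The index pancreatitis case was found without required testing, so the argument reaches enzyme elevations, not clinical pancreatitis. And a loose rule of any post-dose value would count a patient first measured at consolidation as fully observed, and would admit tests prompted by symptoms, which pushes the rate up. The fix has to avoid both.

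**Conclusion.** The point holds as a reporting defect in a secondary safety objective. Required testing began after some patients had received SGN-35 and was phased in over three amendments. The tables of 9.4.1 and 9.5.1 would count any unmeasured patient as having no elevation. The bias is downward, in proportion to the unmeasured share: none if everyone has a post-dose value, and a factor of 0.90 to 0.69 if 5 to 15 of 48 do not. Those counts are assumptions, and the formula assumes equal risk in measured and unmeasured patients, which the mid-trial exclusion may disturb. The actual size can be settled only from the trial's own laboratory records. The primary endpoint, sample size and error rates are not touched.

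**What to change.** 1. Section 9.6.1: add amylase and lipase to the parameters summarised by CTCAE grade.
2. Sections 9.5.1 and 9.6.1: report elevation rates for each enzyme separately, among patients with a protocol-scheduled value drawn after an SGN-35 dose. Show the number tested for lead-in and for consolidation. State which phase the draw before the first consolidation dose belongs to, since on schedule it falls 27 weeks (30 − 3) after the second lead-in dose.
3. List tests prompted by symptoms apart from the scheduled ones.
4. Keep all SGN-35-treated patients as the denominator for clinical pancreatitis. Show those cases descriptively by enrolment before or after Amendment 5, and draw no inference about the exclusion or the monitoring.

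The cost is a few sentences in the analysis section and some extra table columns, with no change to treatment or visits. The denominator may be smaller and the reported rate slightly less favourable. If every patient has a scheduled post-dose value, the rate does not change.

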14.7 Appendix VIII

Data Submission

Study-specific instructions regarding the entry and submission of data using eCRFs through NOTIS will be provided at the time of training prior to study activation. The Internal and Affiliate Data Compliance Policies of the Lurie Cancer Center's DMC regarding will be strictly enforced.

Study Chart & eCRFs

In addition to the regular hospital chart, a separate patient folder will be kept which includes the patient's signed, dated informed consent document. Once a subject is confirmed and enrolled to the study, the following eCRFs should be submitted to the QAM through NOTIS.

Forms to be submitted prior to registration:

Please see Section 4.0 for all forms/documentation to be submitted prior to registration.

Forms to be submitted within 5 days of registration:

- Concomitant Medications Form: updated to reflect the patients' information at the time of registration.
- Adverse Event Forms: update to reflect the adverse events that were present at baseline
- • On-Study Form: dates and results of all baseline exams/tests/labs required to be performed prior to registration will be entered here. Bone Marrow Biopsy Report: upload scanned report under "Bone Marrow Report" in eCRF system
- Cheson Assessment Forms: Enter Measurements for baseline assessment.
- PET/CT Data Form: upload fdg-PET scan (appendix II) under PET/CT Data Form in eCRF system
- FACT-Lym & FACT-Fatigue Forms: upload completed FACT Lym and FACT Fatigue Forms completed at baseline under FACT-Lym & FACT-Fatigue section in the eCRF system
- Cumulative Illness Rating Scale (CIRS): upload completed CIRS form completed at baseline under CIRS section in eCRF system. FACT/GOG Neurotoxicity Form: upload completed FACT/GOG neurotoxicity form completed at baseline under the FACT/GOG Neurotoxicities section in the eCRF system.

ADLs: Print Physician's assessment of ADLs (appendix VI) and upload into the eCRF system.

Forms to be submitted after each cycle of SGN-35 lead-in, after each cycle of AVD therapy, and after each cycle of SGN-35 consolidation therapy:

- Labs Order Form
- Adverse Events Form
- Patient Vitals Form

- Concomitant Medications Form: Should be updated as necessary.
- Treatment Log

Forms to be submitted after SGN-35 lead-in therapy completed (for first 22 patients), after C3D15 of AVD induction, after completion of AVD induction, after completion of SGN-35 consolidation, and every 6 months after patient goes off-treatment:

- Cheson Assessment Form
- PET/CT Data Form: upload fdg-PET scan (appendix II) under PET/CT Data Form in eCRF system

Forms to be submitted after Cycle 1 and Cycle 4 of induction (AVD therapy):

- FACT-Lym & FACT-Fatigue Forms: upload completed FACT Lym and FACT Fatigue Forms completed at Induction C1D1 and Induction C4D1 under FACT-Lym & FACT-Fatigue section in the eCRF system
- FACT/GOG Neurotoxicity Form: upload completed FACT/GOG neurotoxicity form completed at Induction C1D1 and Induction C4D1 under the FACT/GOG Neurotoxicity section in the eCRF system.

Forms to be completed at the end of consolidation:

- Cumulative Illness Rating Scale (CIRS): upload completed CIRS form completed at end of consolidation under CIRS section in eCRF system.
- ADLs: Print physician's assessment of ADLs (appendix VI) and upload into eCRF system.

Forms to be submitted after Cycle 1 of SGN-35 Consolidation, after the completion of SGN-35 consolidation, and 12 months after the completion of SGN-35 consolidation:

- FACT-Lym & FACT-Fatigue Forms: upload in eCRF system.
- FACT/GOG Neurotoxicity Form: upload in eCRF system.

Forms to be completed 6 months after the completion of SGN-35 consolidation:

- FACT/GOG Neurotoxicity Form: upload in eCRF system.

Forms to be submitted when a patient goes off-treatment:

- **Off-treatment Form: Complete part of this form within 1 week the subject's last day of treatment.**

Forms to be completed during Post-Therapy Follow-Up Period:

Labs Order Form: Complete this form every 3 months for 3 years after patient completes therapy
Cheson Assessment Form: Complete this form every 6 months for 3 years after patient completes therapy

FACT-Lym & FACT-Fatigue Forms: upload completed FACT Lym and FACT Fatigue Forms completed under FACT-Lym & FACT-Fatigue section in the eCRF system at 6 months after patient completes therapy and 12 months after patient completes therapy

FACT/GOG Neurotoxicity Form: upload completed FACT/GOG neurotoxicity form under the FACT/GOG Neurotoxicities section in the eCRF system at 6 months after patient completes therapy and 12 Months after patient completes therapy

Follow-Up Form: Complete q 6 months for a period of 3 years after therapy.

Data Submission Table

	Prior to registration	Within 5 days of registration	SGN-35 Lead-In		AVD Induction Therapy						SGN Consolidation Therapy				Follow-up
			C1	C2	C1	C2	C3	C4	C5	C6	C1	C2	C3	C4	
Eligibility Form	X														
Informed Consent Form	X														
Pathology Report	X														
Eligibility Checklist	X														
On-Study Form		X													
Concomitant Medications Form		X ¹	X ⁵	X ⁵						X ⁵					
Patient Vitals Form			X ³	X ³						X ³				X ¹¹	
Labs Order Form			X ³	X ³						X ³				X ¹¹	
AE Form		X ²	X ⁴	X ⁴						X ⁴				X ¹¹	
Treatment form			X ⁶	X ⁶						X ⁶					
Bone Marrow Biopsy Report Upload		X ⁷													
CIRS Form Upload		X												X ¹³	
FACT/GOG Neurotoxicity Upload		X				X ¹²			X ¹²			X ¹⁵		X ¹³	X ¹⁶
FACT-Lymp and FACT-fatigue upload		X				X ¹²			X ¹²			X ¹⁵		X ¹³	X ¹⁷
ADL Assessment	X ²⁰												X ²⁰		
PET/CT Data Form Upload	X			X ⁸			X ⁹			X ¹⁰			X ¹³	X ¹⁸	
Cheson Assessment Form				X ⁸	X ⁷		X ⁹			X ¹⁰			X ¹³	X ¹⁸	
Off-Treatment Form													X ¹⁴		

Follow-Up Form	X ¹⁹
----------------	-----------------

- 1 Should reflect medications taken at baseline
- 2 Should reflect all AEs present at baseline
- 3 Enter by end of each cycle, for assessments conducted on D1 of each cycle.
- 4 Update after each physical exam and labs done on D1 of each cycle, and as needed.
- 5 Update as required
- 6 To be entered at the end of each cycle
- 7 Should reflect bmbx results required at baseline. If bmbx is positive at baseline, repeat biopsies should be done, and reports uploaded at time of CR and relapse.
- 8 Upload completed forms after end of SGN lead-in cycle 2, PET/CT Data Form only for the first 22 patients.
- 9 Upload completed forms by at the end of cycle 3 (for assessment required C3D15).
- 10 Uploaded completed forms for assessment required at the end of AVD therapy.
- 11 Enter q 3 months for a period of three years after pt completes therapy.
- 12 Submit by end of C1 and C4 for assessments conducted at D1 of C1 and C4.
- 13 To be completed and uploaded at the end of consolidation.
- 14 To be completed 1 week within 1 week of when subject goes off-treatment.
- 15 To be completed and uploaded by the end of C1 of consolidation.
- 16 To be completed and uploaded 6 months and 12 months after completion of consolidation.
- 17 To be completed and uploaded 12 months after the completion of consolidation.
- 18 To be completed and uploaded q 6 months for a period of 3 years.
- 19 Complete follow-up form for a period of 3 years after pt goes off treatment.
- 20 Print physician's assessment of ADLs (appendix VI) and upload into the eCRF system.
